4.5. Antibody analysis

4.5.1. Auto-antibody analysis

Anti-Nuclear Antibodies (ANA) will be described in a contingency table comparing ANA modalities at baseline with ANA modalities at W013 thus allowing to determine number and percentage of patients moving from one modality to another between baseline and W013.

In a same way, Anti-Sjögren's Syndrome A Antibodies (Anti-SSA), subtype Anti-SSA RO52 and subtype Anti-SSA RO60 as well as Anti-Sjögren's Syndrome B Antibodies (Anti-SSB) will be described in a contingency table comparing Positive/Negative modalities at baseline with Positive/Negative modalities at W013.

Rheumatoid Factor (RF) will be described as value at baseline and W013 and change from baseline to W013.

4.5.2. Anti-Drug Antibody analysis

Number and percentage of patients having respectively positive or negative Anti-Drug Antibodies (ADA) will be described by treatment group at each visit on the W000-W028 period.

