Immunogenicity

No anti-S95011 antibodies (Abs) were formed after single IV. infusion of S95011 0.002 mg/kg and 0.02 mg/kg. Abs were formed as of Day 15 (0.2 mg/kg; 1 subject), Day 29 (1 mg/kg; 2 subjects and 4 mg/kg; 1 subject), or FU1-Day 71 (10 mg/kg; 2 subjects). The last sampling timepoint the Abs were present was Day 43 (0.2 mg/kg; 1 subject), FU1-Day 71 (1 mg/kg; 4 subjects), FU2-Day 85 (4 mg/kg; 6 subjects), or FU4-Day 113 (10 mg/kg; 5 subjects).

After s.c. administration (1 mg/kg), Abs were formed on Day 29 (2 subjects) and present until FU1-Day 71 (4 subjects).

In Part 2, Abs were formed on Day 57 (6 mg/kg; 1 subject) or FU2-Day 85 (10 mg/kg; 1 subject) and were present until FU5-Day 127 (6 mg/kg; 6 subjects) or FU6-Day 141 (10 mg/kg; 5 subjects).

To date, no safety concern arose either from the non-clinical safety studies or from the clinical study.

Study design

This is a proof-of-concept, phase IIa study.

This study is designed to evaluate preliminary therapeutic efficacy of multiple intravenous infusions of 750 mg of S95011, the safety, tolerability, pharmacokinetics and pharmacodynamics in patients with primary Sjögren's syndrome.

This phase IIa study is a prospective, international, multicentre, randomised (2:1), double-blind, placebo-controlled study. It is expected to include 45 patients (30 receiving S95011, 15 Placebo).

A randomized, placebo-controlled, double-blind approach is used to eliminate potential bias in reporting clinical efficacy and safety data in this first exploratory study in pSS patients. Patients will be randomized to S95011 or placebo in a 2:1 ratio in order to minimize exposure to placebo and to gather more data on S95011. Stratified randomization is done in order to limit imbalances between active and placebo arms in baseline intake of oral corticosteroids and baseline intake of antimalarials. The placebo to S95011 will be used as comparator to provide objective clinical efficacy as well as safety data generated from patients exposed to the experimental therapy. Since there is no established, clinically effective disease modifying treatment for patients with pSS, potential treatment with placebo (on top of standard of care therapy, if necessary) is justified.

Study Population

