3.2. Secondary objectives

The secondary objectives are:

To evaluate efficacy of multiple intravenous (IV) infusions of 750 mg of S95011 compared to placebo after 13 weeks of treatment on:

- Patient's symptoms using EULAR Sjögren Syndrome patient reported Index (ESSPRI)
- Fatigue using the Multidimensional Fatigue Inventory (MFI)
- Quality of life (QoL) using Short Form Health Survey (SF-36)
- Physician's global assessment (PhGA) of the disease activity using a 0 to 10 numerical rating scale (NRS)
- Patient's global assessment (PGA) of the disease activity using a 0 to 10 numerical rating scale (NRS)
- Tear gland function using the Schirmer test
- Tear gland function using Ocular Staining Score (OSS)

- Salivary gland function measured by sialometry under unstimulated and stimulated conditions

To assess the safety and tolerability of multiple intravenous infusions of S95011,

To assess the pharmacokinetics (PK) of S95011 in serum,

To assess pharmacodynamics [receptor occupancy (RO)] of S95011 in blood,

To determine the incidence of anti-drug antibodies (ADA) formation.

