3.4. Endpoints

See [Sections 7, 8 and 9](#) for more details

Primary efficacy endpoint:

Change from baseline in ESSDAI total score to W013

Secondary efficacy endpoints:

- ESSDAI score by domain and total score at each visit (value & change)
- ESSPRI score by symptom and total score at each visit (value & change)
- Proportion of patients with ≥ 3 points, ≥ 5 points, ≥ 7 points of improvement from baseline in ESSDAI at each visit
- Proportion of patients with ≥ 1 point, ≥ 2 points, ≥ 3 points of improvement from baseline in ESSPRI at each visit
- Proportion of patients with ≥ 3 points of improvement in ESSDAI and with ≥ 1 point of improvement in ESSPRI from baseline at each visit
- Fatigue (MFI), quality of life (SF-36), physician and patient's global assessment of the disease activity (NRS) at each visit (value and change)
- Tear gland function: Schirmer's test and in OSS at each visit (value and change)
- Salivary gland function: unstimulated and stimulated salivary flow rate at each visit (value and change)

Other secondary endpoints:**- Safety:**

The safety and tolerability assessed by incidence of adverse events (AEs), change over time in safety parameters (vital signs, ECG, biological laboratory) and incidence of abnormal safety parameters throughout the study.

- Pharmacokinetics

Pharmacokinetics of S95011 in serum

- Pharmacodynamics

Receptor Occupancy (RO) of S95011 in blood

- Incidence of ADA**Exploratory endpoints:****- In blood:**

- Lymphocytes subsets (PBMC)
- Some proteins involved in pSS physiopathology (IL-7, cytokines, specific proteins ...)
- Cytokine release panel
- Immune panel, auto antibody-panel, β 2 microglobulin.

- In salivary glands:

- Lip biopsy for salivary gland collection (S95011 concentration, exploratory histology and exploratory biomarkers assessments) (optional biopsy at W013).

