9.4. Measurement of anti-drug antibodies (ADA)

To determine the incidence of anti-drug antibodies (ADA) formation, blood samples (3 mL/time-point) will be collected for all patients:

ADA will be measured in serum samples taken pre-dose (before the start of the IMP infusion) at W000, W002, W004, W007 and W010, and at W013, W019, W028.

ADA formation will be determined using S95011-specific ADA assays, by a bioanalytical laboratory under the responsibility of the Sponsor, using a validated bioanalytical method. The bioanalytical procedure will be described in a separate bioanalytical protocol. The randomisation list will be sent to the bioanalytical centre in order to select the samples to be analysed.

All the procedures for sampling, labelling, handling, storage and shipment will be described separately in a laboratory manual. All samples should be collected at the time specified and properly labelled. Samples missed or lost for any reason should be recorded.

For each sample, the theoretical and exact dates and times at which the study drug is lastly administered should be reported in the requisition form in addition to the exact dates and times of serum sample collection.

ADA samples will be destroyed after their analysis or at the latest at study end. ADA back-up samples will be stored in the biorepository, if agreed by the patient (specific optional informed consent signed) (See [Section 9.5.3](#)).

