9.5.3. Transfer of analytical results

Final analytical results will be transferred to Data Management according to [Section 14.3](#).

All mandatory samples will be destroyed after analysis or at the latest at study end. However, if agreed by the patient (specific optional informed consent signed), optional samples may be stored in suitable conditions after study completion in a central bio-repository for a maximum duration of 25 years (except for ADA back-up samples which will be stored up to 15 years maximum): Indeed, after the end of the study, if a specific optional informed consent form is signed, the samples may be used for other parameters assessments in relation to the study drug or to pSS in light of scientific knowledge or technology unknown today but that may appear in the literature in the coming years or extend the search for the potential of other relevant biomarkers. After the trial, in addition to the biomarkers specified above, exploratory biomarker research may be conducted on any remaining and /or back up samples collected for PBMCs and blood investigations. In particular, it may concern PBMCs samples, samples collected for the PK, ADA, IL7 analyses and samples dedicated to other proteins investigations.

Back-up samples for anti-drug antibodies (ADA) will be stored for a maximal period of 15 years to allow complementary analyses as part of the drug immunogenicity assessment. This could include ADA reanalysis with a modified bioanalytical method, new methods to characterize pre-existing ADA or the neutralizing potential of ADA or any other method used to study ADA or their impact on safety or efficacy.

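### SAP 4.5.2 tabulates ADA status visit by visit only, so it does not in general yield the incidence of ADA formation named in the objective

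*SAP*

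**What the plan says.** - **Objective.** Protocol 3.2 lists among its secondary objectives "To determine the incidence of anti-drug antibodies (ADA) formation", and SAP 1.1.1 repeats it. Protocol 3.4 names the endpoint as "Incidence of ADA".
- **Sampling.** Protocol 9.4 takes ADA samples "at W000, W002, W004, W007 and W010, and at W013, W019, W028". The W000 sample precedes the first infusion, so there is one baseline result and seven later ones per patient.
- **Analysis.** SAP 4.5.2 is a single sentence. It gives the number and percentage of patients "having respectively positive or negative Anti-Drug Antibodies (ADA) will be described by treatment group at each visit", from W000 to W028. Protocol section 10 contains no ADA analysis, and SAP section 6 announces no change on ADA.
- **Not defined in either document.** There is no definition of an ever-positive or newly positive patient, no rule for patients positive at W000, no denominator, and no named analysis set for ADA.
- **Neighbouring section.** For ANA, anti-SSA and anti-SSB, SAP 4.5.1 plans baseline-by-W013 contingency tables, "thus allowing to determine number and percentage of patients moving from one modality to another between baseline and W013". ADA has no such table.

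**The concern.** Formation is a change within a patient: negative before treatment, positive afterwards. A percentage positive at a visit is a point prevalence. It does not say whether the positives at two visits are the same people, or whether someone positive at W013 was already positive at W000.

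Protocol section 2 lists immunogenicity among the reactions to be closely monitored and says that extrapolating the risk from healthy subjects to pSS patients is unknown. This trial is therefore the first source of a patient-level ADA rate in the disease. If the SAP is followed to the letter, that rate is not among its outputs. Anyone who later wants it would have to choose the definition and the denominator after unblinding.

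**Working it through.** The documents state no ADA rate or precision target, so there is no planned figure to reproduce. The check is how far the planned table pins down incidence.

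**Inputs**
- Group size n = 30 on S95011 (protocol synopsis and 10.2).
- Post-baseline ADA visits: W002, W004, W007, W010, W013, W019, W028, so seven (protocol 9.4).
- Assumed for illustration: complete data; positive counts c1 to c7 at those visits; b patients positive at W000.

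**Formulas**
- Patients ever positive after baseline lie between max(c) (the same people each time) and min(n, sum of c) (different people each time).
- Newly positive patients, among the n − b negative at W000, lie between max(0, max(c) − b) and min(n − b, sum of c).

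**Results**

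| Assumed counts at the seven visits | b | Quantity | Lower | Upper |
|---|---|---|---|---|
| 1 at each (sum 7) | not used | ever positive | 1/30 = 3.3% | 7/30 = 23.3% |
| 3 at each (sum 21) | not used | ever positive | 3/30 = 10% | 21/30 = 70% |
| 0, 0, 1, 2, 3, 4, 3 (sum 13) | not used | ever positive | 4/30 = 13.3% | 13/30 = 43.3% |
| 3 at each (sum 21) | 3 | newly positive | 0/27 = 0% | 21/27 = 77.8% |

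In the last row the lower end has the three W000 positives staying positive and nobody converting. The upper end has those three turning negative and 21 others positive once each. The planned table looks identical in both cases: 3 positive at every visit, W000 included.

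**When the table is enough.** If there are no positives after baseline, incidence is 0. If every positive patient stays positive to W028 and no result is missing, the W028 count is the ever-positive count and the W028 count minus b is the newly positive count. Outside such cases the table gives only a range.

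**How close to persistence is this drug likely to be?** Protocol section 2 (Immunogenicity) gives phase I counts at first appearance and at the last sampling with antibodies present:
- multiple dose, 6 mg/kg: 1 subject at Day 57, 6 at Day 127;
- multiple dose, 10 mg/kg: 1 at Day 85, 5 at Day 141;
- single dose, 4 mg/kg: 1 at Day 29, 6 at Day 85.

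The counts build up, which favours the lower ends of the ranges. Individual courses are not reported, so turnover between patients cannot be excluded.

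**Comparison within the SAP.** Emergent laboratory abnormality is defined against baseline (SAP 3.2) and counted as patients with at least one such value (SAP 4.4.2.1). Adverse events have a treatment-emergent definition and a count of patients with at least one (SAP 4.4.1). ADA, where the objective itself speaks of formation, has neither element.

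**The case against.** - **The table includes W000.** A reader might infer that pre-existing positives are counted as formed on study and that incidence is therefore overstated. The documents do not support this. The pre-dose W000 column shows baseline prevalence, and a flat percentage from W000 onwards would not be read as new formation. What remains is that the table cannot separate stable positivity from turnover.
- **Positivity probably persists.** The phase I counts suggest so, and late prevalence at W019 and W028 may then track cumulative incidence fairly well. This stands, and it makes the upper ends of the ranges logical limits rather than expectations.
- **The endpoint can be read by visit.** SAP 1.1.2 gives the ADA endpoint followed by the list of sampling visits, and the planned table fits that layout. The mismatch is with the objective's reference to formation, which both documents keep.
- **Pre-existing ADA may be rare.** Protocol 9.5.3 mentions "new methods to characterize pre-existing ADA" only as possible later work on back-up samples. It is no evidence that baseline reactivity is expected here. Linking patients across visits is still needed if nobody is positive at W000.
- **Table templates are separate.** SAP section 1 places them in another document, which may hold an overall row. That cannot be checked, so the point concerns the SAP text. The definition and denominator belong in the SAP in any case.
- **Nothing is lost.** Patient-level results allow incidence to be derived at any time. This is correct, and it is why this is a gap in the planned summary and not in data collection.

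**Conclusion.** The point holds as a gap between objective and analysis. As written, SAP 4.5.2 yields point prevalences, and these fix the incidence of ADA formation only in special cases. Under assumed counts of 3 per post-baseline visit in 30 patients with complete data, the same table fits 10% to 70% ever positive and, with 3 positive at W000, 0% to 77.8% newly positive. These are limits, not forecasts; persistent positivity would bring the truth near the lower end.

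A stronger reading would be that the trial cannot deliver ADA incidence at all. The documents do not support it, because all eight samples per patient are planned. The matter concerns a descriptive secondary endpoint and touches neither the primary analysis nor the sample size. It should be corrected because the correction is cheap and is best fixed before unblinding.

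**What to change.** Add to SAP 4.5.2, by treatment group:

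1. The number and percentage of patients ADA-negative at W000 with at least one positive result after the first infusion, up to W028. The denominator is W000-negative patients with at least one such result. An exact confidence interval is optional.
2. Patients positive at W000, reported separately. Use a titre-rise rule for them only if the assay reports titres; neither document mentions ADA titres.
3. The analysis set used and the number of patients without a W000 result or without any later result.

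Keep the by-visit table. The cost is one descriptive table from data already collected, with no new samples and no change to any efficacy analysis.

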4.6. Exploratory analysis

Not applicable.

4.7. Biomarkers analysis

4.7.1. Biomarker endpoints: Interleukin 7 cytokine (IL7), cytokines and other proteins involved in pSS physiopathology

Interleukin 7 cytokine is evaluated at W000, W002, W004, W007, W010 W013, W019 and W028 by MSD Simplex. Pro-inflammatory panel (IL10, TNF-a, IFN γ , IL2, IL6, IL8, IL4, IL1b, IL12p70 & IL13) is evaluated at W000, W002, W004 and W013 by MSD full multiplex. The cytokine panel (GM-CSF, IL1a, IL5, IL16, IL12/IL23p40, IL15, IL17A, TNF-b, VEGF) is evaluated at W000, W004 and W013 by MSD Multiplex. The chemokine panel (IP10 and MCP-1) is evaluated at W000, W004 and W013 by MSD multiplex. CXCL9, CXCL11 and CXCL13 is evaluated at W000, W004 and W013 by Quantikine ELISA kit.

In case of premature withdrawal, an evaluation is planned at this time-point and the evaluation will not be described in the following analysis.

Biomarker results will be described for patients of the Biomarker Set (BMKS).

For descriptive statistics, marker will be expressed in terms of concentration at baseline and at each post baseline visit and relative change from baseline to post baseline visit.

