Five studies have been conducted with GSK 26118960 and PF 06342674 in around 150 people including at least 98 healthy volunteers with administered single or multiple weekly doses from 0.25 mg/kg to 6 mg/kg IV or SC. Two of these studies (Ellis *et al*, 2018; Herold *et al*, 2019) have been published and partial results from the other studies can be found on <https://clinicaltrials.gov>. (NCT01808482; NCT02293161; NCT01740609; NCT02045732; NCT02038764). No significant adverse event nor adverse drug reaction has been described within the available information.

Up to now, no safety issue in the phase 1 study in healthy volunteers was reported with S95011. However, due to its nature, IV administration and mechanism of action, the following reactions will be closely monitored:

- Acute hypersensitivity

Humans administered with foreign proteins are at risk of developing allergic reactions, including anaphylaxis. Patients can present with the following symptoms: itching, flushing, headache, nausea/vomiting, hypotension, urticaria, bronchospasm, or angioedema.

- Infections

Subjects treated with S95011 may be at an increased risk of infection. Administration of S95011 could be expected to result in immunomodulation with a decreased capacity to mount a response to novel immunogens, including those of bacterial, viral, fungal and parasitic origin when full receptor occupancy has been achieved.

- Cytokine release syndrome

No cytokine release has been observed in FIH study (IFN γ , IL12p70, IL4, IL5, IL6, IL8, TNF α). However, given the risk of cytokine release syndrome observed in certain therapeutic monoclonal antibodies, this event cannot be ruled out in patients treated with S95011.

- Vaccination

Vaccination of patients during treatment with S95011 and prior to clearance of S95011 is likely to result in non-protective vaccinal antibody titers due to the pharmacologic activity of the antibody.

- Immunogenicity

Extrapolation of immunogenicity risks from healthy subjects to pSS patients is unknown.

- Lymphopenia

No clinically significant lymphopenia has been observed neither in the phase 1 study nor in preclinical studies. However, due to S95011 mechanism of action, a possible lymphopenia cannot be ruled out.

The possible risks and their mitigations are presented in the table below.

Risks	Mitigations

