2 At each ESSDAI assessment, cryoglobulins measurement will be performed locally and the result will be used for ESSDAI scoring. Cryoglobulin result obtained from a previous sampling performed within 1 month before screening visit could be used for ESSDAI scoring at screening. In case of presence of cryoglobulinaemia, cryoglobulin will be identified (type I, II or III). In addition, for assessments not listed in the protocol as mandatory tests but which may be needed to estimate ESSDAI, including Chest X-ray, pulmonary high resolution computer tomography (HRCT), lung function test (Diffusing-capacity of the lung for carbon monoxide (DLCO), forced vital capacity (FVC)), estimated glomerular filtration rate (eGFR), electromyography (EMG), muscle (or any other) biopsy, it is at the investigator's discretion to have these assessed based on the signs and symptoms of the patient so to provide correct ESSDAI readout (see [section 7.2](#)).

3 If ASSE blood samples for haematology and biochemistry are performed more than 14 days before W000, blood samples for blood cell count and CRP must be repeated (central or local) within a maximum of two weeks before W000. These tests repeated should be obtained within the allowed screening period, and must be considered for the patient inclusion.

4 Blood samples for biochemistry/haematology will be performed after 10 hours fasting.

5. Only in women of childbearing potential

For all blood samples planned at visit with IMP administration, only one pre-dose sample has to be performed (before Investigational medicinal product (IMP) administration. Except for :

6. **PK samples:** One pre-dose sample (before IMP) + 2 post dose samples (one right after the end of the infusion and one in the [1-3h] interval after the end of the IMP infusion at W000 and W010

7. **Receptor occupancy (RO) samples:** One pre-dose sample (before IMP) and one sample right after the end of the infusion of the IMP (just after PK sample) at W000 and W010

8. **Cytokine release panel:** One pre-dose sample (before IMP) and one post-dose sample right after the end of IMP infusion at W000 and W002

9. Lip biopsy can be performed the day before and up to 2 days after the scheduled visit's date. In any case sialometry has to be performed before biopsy. The consent for participating in the lip biopsy can be proposed an other time to the patients during the course of the study until W013

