9.5.1. Assessments in blood

Participation in the CL2-95011-001 study implies a systematic participation in the mandatory investigation. All patients will have to consent to this investigation by signing the main information and consent form for participation in the study.

In addition, in case of consent withdrawal, related samples will be destroyed after mandatory assessment is completed and at the latest at study completion.

Lymphocytes subsets (PBMC):

Lymphocytes subsets will be measured on PBMC at W000, W004, W007, W013.

The lymphocytes subsets panels analysis will be subcontracted to a central laboratory. The details for sampling, handling, storage and shipping of the samples will be described in a laboratory manual.

Results will be directly transferred in the sponsor database by the central laboratory, without communication to the investigator.

PBMC samples will be destroyed after their analysis or at the latest at study end. PBMC back-up samples will be stored in the biorepository, if agreed by the patient (specific optional informed consent signed) (See [Section 9.5.3](#)).

IL-7, cytokines and other proteins involved in pSS physiopathology

IL-7 and some cytokines (for instance may include but not limited to and according to the analytical assays used IL-12/IL-23p40, IL-15) will be measured at W000, W002, W004, W007, W010, W013, W019, W028.

Other specific proteins (may include but not limited to and according to the analytical assays used CXCL13, IFN- γ , IL-2, IL-4, IL-6, IL-17, TNF α ,....) will be measured at W000, W004, W013.

Cytokine release panel: IFN- γ , IL-2, IL 6, IL-8, IL-10, TNF- α concentrations and may include other proteins according to the analytical assays used.

Will be performed at W000, W002:

- One pre-dose sample (before IMP)
- and one post-dose sample right after the end of the IMP infusion.

The exploratory protein and cytokine panels analysis will be subcontracted to a central laboratory. The exact list of the proteins measured, the details for sampling, handling, storage and shipping of the samples will be described in a laboratory manual. In order to limit the amount of blood collected, the same sampling will be used for assessing several proteins.

Results will be directly transferred in the sponsor database by the central laboratory, without communication to the investigator.

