10.1.2.6. Exploratory markers analysis

Cell subsets:

The count of cell subsets will be described using value at each time point and by treatment group.

IL-7, cytokines, and other proteins in blood:

Concentration of circulating proteins will be described using value and by classes (< LLOD, [LLOD ; ULOD], > ULOD) at each time point and by treatment group. Proteins with concentration below LLOQ in more than 70% of all samples will be excluded from analysis

Immune panel, β 2 microglobulin and on the auto-antibody panel:

Concentration of immune panel, β 2 microglobulin and auto-antibody panel will be described using value at each time point and by treatment.

Salivary glands tissue:

Histological analyses and exploratory biomarkers will be described by treatment group.

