 - IL-7 and some cytokines measured at W000, W002, W004, W007, W010, W013, W019, W028.
 - Other specific proteins involved in the pSS physiopathology will be measured at W000, W004, W013.
 - Cytokine release panel at W000 and W002.
 - Immune panel at ASSE (Selection visit), W000, W004, W013.
 - Auto antibody-panel at ASSE, W013.
 - β 2 microglobulin at W000, W004, W013.
- **In salivary glands:**
 - Lip biopsy for salivary gland collection (S95011 concentration, exploratory histology and exploratory biomarkers assessments) (optional biopsy at W013).

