3.2. General definitions

Patients having taken at least one dose of IMP correspond to patients with at least one date of first and/or last IMP intake complete or partially complete.

Analysable value will be defined as any non-missing value, except for:

- Laboratory parameters:
 - A laboratory value is considered as analysable if non-missing and not flagged in the ClinTrial database as "not analysable".
 - Vital signs value is considered as analysable if collected under appropriate circumstances (corresponds to the item of the source database).

Baseline value will be defined as the last analysable value prior to the first IMP intake. In case of patient included and/or randomised but not having taken at least one dosage of IMP: value at baseline is defined as the last analysable value prior or equal to date of inclusion visit.

Considered periods are:

- ASSE-W013 period.
- ASSE-W028 period.

Last post-baseline value under treatment of the period will be defined as the last post-baseline analysable value under treatment during the considered period.

Change from baseline to post-baseline visit is calculated as: Value at the post-baseline visit - Value at baseline.

Change from baseline to post-baseline visit under treatment is calculated as: Value at the post-baseline visit under treatment - Value at baseline.

Change from baseline to last post-baseline value under treatment is calculated as: Last post-baseline value under treatment - Value at baseline.

For safety endpoints (except adverse events), the following definition will be applied:

- **High emergent abnormal value under treatment according to the laboratory reference ranges** is defined as value \leq ULN (Upper Limit of Normal laboratory reference range) or missing at the baseline of the treatment period and $>$ ULN under treatment.
- **Low emergent abnormal value under treatment according to the laboratory reference ranges** is defined as value \geq LLN (Lower Limit of Normal laboratory reference range) or missing at baseline of the treatment period and $<$ LLN under treatment.

- **High emergent abnormal value under treatment according to the cut-offs for PCSA** values is defined as value \leq ULS (Upper Limit used to define potentially clinically Significant abnormal values) or missing at baseline of the treatment period and $>$ ULS under treatment.

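### For the exploratory cytokine release panel, SAP 4.7.1 specifies by-arm summaries only at baseline and per post-baseline visit, so the pre- and post-infusion samples at W000 and W002 get no defined time points and no within-infusion change.

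*SAP*

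**What the plan says.** **Sampling.** Footnote 8 to the investigation schedule (protocol 4.1.2) asks for "One pre-dose sample (before IMP) and one post-dose sample right after the end of IMP infusion at W000 and W002". Protocol 9.5.1 repeats the pairing and names the six analytes.

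**Endpoint.** Protocol 3.4 lists the cytokine release panel among the exploratory endpoints. SAP 1.1.2 keeps it as "Cytokine release panel at W000 and W002", without the pre/post timing.

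**Planned description in the protocol.** Section 10.1.2.6 states: "Concentration of circulating proteins will be described using value and by classes", at each time point and by treatment group. It names no post-minus-pre change.

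**Planned description in the SAP.** Section 4.7.1 puts all six analytes in a pro-inflammatory panel that "is evaluated at W000, W002, W004 and W013 by MSD full multiplex". The summary rule is that the "marker will be expressed in terms of concentration at baseline and at each post baseline visit and relative change from baseline to post baseline visit". Section 4.7.1.2.2 repeats this by arm and by visit. Section 3.2 adds: "Baseline value will be defined as the last analysable value prior to the first IMP intake". Section 4.7.1.1 gives the percentage of values below, within or above the quantification limits, pooled overall. If more than 30% are out of range, the quantitative analysis is not done, and a breakdown by group or visit is optional.

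**Declared changes.** SAP section 6 records that salivary gland tissue and PBMC subsets will not be analysed. It says nothing about the cytokine release panel.

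**The concern.** Cytokine release is a rise within one infusion. The samples that can show it are the two drawn on either side of that infusion, and a summary by visit does not compare them.

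Protocol section 2 says of cytokine release syndrome that "this event cannot be ruled out in patients treated with S95011", and this is the first study of the product in patients with primary Sjögren's syndrome. Protocol 9.5.1 sends the results of this panel straight to the sponsor database and not to the investigator, so they will be read in the statistical output or not at all. The local assay described in protocol 8.6 is triggered only by a clinical suspicion. It does not replace a systematic look at all patients in both arms. If the SAP is followed literally, the study collects placebo-controlled paired samples at first exposure and may then report no paired result by arm.

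**Working it through.** The check is a comparison of texts and a count of samples. The plan states no figure to reproduce.

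**Count.** Inputs: 45 planned patients, 30 on S95011 and 15 on placebo (protocol synopsis); 2 infusions with paired sampling; 2 samples per infusion (protocol 4.1.2, footnote 8).

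- Samples: 45 × 2 × 2 = 180.
- Pairs: 45 × 2 = 90, made up of 30 × 2 = 60 on S95011 and 15 × 2 = 30 on placebo.
- W000 post-infusion samples: 45 × 1 = 45.

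These are planned numbers and assume that every sample is obtained.

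**Where each sample lands under the SAP rules.**

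| Sample | Role under SAP 3.2 and 4.7.1 | By-arm quantitative output |
|---|---|---|
| W000 pre-dose | Baseline, where sampling times are available | Yes |
| W000 post-infusion | Neither baseline nor a post-baseline visit | None clearly specified |
| W002 pre-dose | One of two values at a post-baseline visit | Undetermined |
| W002 post-infusion | The other value at the same visit | Undetermined |

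**What the W002 row would show.** The only contrast defined is change from the W000 baseline. If the W002 pre-dose value is used, the row shows the state two weeks after the first dose. If the W002 post-infusion value is used, it mixes that two-week change with the effect of the second infusion. Neither is the change within the W002 infusion.

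**Rules that might be borrowed.**

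- SAP 7.2.3.2, written for clinical laboratory data, keeps the first analysable value at a visit. Applied here, it would select the W002 pre-dose value and leave the post-infusion value out of the by-visit table.
- SAP Table (7.1.1) 1 treats an assessment without a recorded time as prior to treatment if it is dated on the day of first intake. Under that rule a W000 post-infusion value could qualify as baseline. In protocol 9.5.1 the instruction to record exact sampling times stands in the paragraph on β2 microglobulin, so it is not clear that times exist for this panel.

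**Internal comparison.** SAP 4.4.3.1 lists blood pressure and heart rate before infusion and also 2 hours after infusion at W000 and W002. The same document therefore separates pre and post values where its authors wanted both. Section 4.7.1 has no such wording.

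**Result.** Of the two within-infusion contrasts per patient, the SAP clearly specifies neither. The W002 contrast is absent; the W000 contrast is at best arguable, as discussed under the objection.

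**The case against.** The strongest case against has five parts.

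1. **The W000 post-infusion values are not wholly unused.** The class percentages in SAP 4.7.1.1 cover values of the marker without restricting them by time, so these samples may be counted there. This stands. A reader might infer that they enter no summary at all, and the documents do not support that. What is missing is a by-arm or time-point summary.
2. **SAP 4.7.1.2.1 speaks of change from baseline to a post-baseline time point.** On that wording W000 post-infusion could be such a time point, and its change from the W000 pre-dose baseline would be the within-infusion change. This stands in part. The same sentence ends by referring to values at the visits, and the output section 4.7.1.2.2 is purely by visit. The W000 contrast is therefore ambiguous and cannot be called excluded. The phrase does nothing for W002.
3. **The protocol never promised a post-minus-pre change.** This is correct. A reader might infer that a planned contrast was dropped. The undeclared change is narrower: description by time point became description by visit.
4. **Table templates are in a separate document, and SAP section 1 says that some exploratory objectives are outside its scope.** An output could exist there. However, section 4.7.1 does cover these analytes and sets their summary rule, so the scope statement does not explain the gap, and templates should follow the SAP.
5. **Impact is limited.** The endpoint is exploratory and descriptive, with 15 placebo patients. Clinical cytokine release syndrome is an event of special interest (protocol 8.6), immediately notifiable (8.7) and tabulated (SAP 4.4.1). All of this stands. The documents do not support a reading that cytokine release goes unmonitored, or that this panel could by itself exclude subclinical release.

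**Conclusion.** The point holds for the exploratory cytokine release panel, which is the SAP's pro-inflammatory panel. It does not concern what SAP 4.7.1 calls the cytokine panel, which holds other analytes measured at W000, W004 and W013.

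The SAP keeps an endpoint whose design is paired sampling but specifies only visit-level output by arm. Three things are missing: a by-arm row for W000 post-infusion, a rule for the two W002 values, and any stated within-infusion change. The size is up to 90 planned pairs. If more than 30% of values are out of range, no by-arm result is guaranteed for this panel in any form.

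The conclusion rests on the SAP text alone, since the table templates were not available. It has no bearing on the primary or secondary efficacy analyses or on the reporting of clinical cytokine release syndrome. It is still worth correcting, because following the rule as written leaves the endpoint unanswered at a point where the correction is nearly free.

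**What to change.** In SAP 4.7.1 and 4.7.1.2.2:

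- Define W000 pre-dose, W000 post-infusion, W002 pre-dose and W002 post-infusion as four separate time points for the six analytes of the cytokine release panel.
- Describe by arm the value at each time point and the within-infusion change, post versus pre, at each of the two infusions.
- If the 30% rule in 4.7.1.1 stops the quantitative analysis, give by-arm counts below, within and above the quantification limits at these four time points as a required output.
- State that only pre-dose values serve as baseline and feed the by-visit change from baseline. Identify the W000 samples by their pre/post label so that the rule for assessments without a time cannot make a post-infusion value the baseline.
- Note in section 6 the move from time points to visits, or remove it by adopting the wording above.

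The cost is a paragraph of SAP text and one or two descriptive tables on samples already scheduled. No new sample is needed.
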